6.4. Study Intervention Compliance

Participants will receive a single treatment of BOTOX under the direct supervision of study site personnel.

The study site will keep an accurate drug disposition record that specifies the amount of study intervention administered to each participant and the date of administration.

6.5. Concomitant Therapy

Study center staff must notify the sponsor immediately if a participant consumes any concomitant medications not permitted by the protocol. Participants who admit to using prohibited concomitant medications may be discontinued from the study at the discretion of the investigator or the sponsor.

The use of any concomitant medication or vaccine, (including prescription or over-the-counter medication, vitamins and/or herbal supplements), is to be recorded on the participant's eCRF at each visit along with the reason the medication is taken.

Concomitant therapy and/or medications considered necessary for the study participant's welfare may be given at the discretion of the investigator.

If concomitant medications may have an effect on efficacy or safety outcomes, these medications should be administered in dosages that remain constant throughout the course of the trial at the discretion of the investigator.

If the permissibility of a specific medication/treatment is in question, please contact the sponsor.

6.5.1. Prohibited Interventions and Washout Before the Study

Refer to eligibility criteria (exclusion criteria, Section [5.2](#)).

6.5.2. Permitted Interventions

Any medication or vaccine (including over-the-counter or prescription medicines, vitamins, and/or herbal supplements) that the participant is receiving at the time of enrollment or receives during the study must be recorded along with:

- Indication/reason for medication use
- Dates of administration including start and end dates
- Dosage information including dose and frequency

Therapy considered necessary for the participant's welfare may be given at the discretion of the investigator. If the permissibility of a specific concomitant or prior medication/treatment is in question, please contact the sponsor.

BOTOX

Any medication taken during the study between the date of study intervention and the date of the EOS visit will be recorded in the eCRF as a concomitant medication; any medication started after the EOS visit will not be considered a concomitant medication and should not be captured in the eCRF.

6.5.3. Prohibited Interventions During the Study

The decision to administer a prohibited medication/treatment during the study period is done with the safety of the study participant as the primary consideration. When possible, the sponsor is to be notified before the prohibited medication/treatment is administered.

**6.6. Dose Modification**

No dose modifications are permitted.

6.7. Intervention after the End of the Study

No interventions after the end of study are planned.

7. Discontinuation of Study Intervention and Participant Discontinuation/Withdrawal

A premature discontinuation will occur if a participant who signs the ICF and is randomized ceases participation in the study, regardless of circumstances, before the completion of the protocol-defined study procedures.

BOTOX

Notification of early participant discontinuation from the study and the reason for discontinuation will be made to the sponsor and will be clearly documented in the appropriate eCRF.

The sponsor should be consulted in advance of withdrawal whenever possible. Every effort should be made to retain participants in the study until completion as much as possible. Participants who are withdrawn from the study may not be re-enrolled but will be asked to undergo all early withdrawal activities. Definitions of the standard terms are provided in [Appendix 5](#).

Reasons for discontinuation from the study treatment and/or the study may include the following commonly used or other acceptable terms:

Commonly Used Terms	Other Acceptable Terms
Adverse event	Death
Completed	
Lost to follow-up	
Other	
Physician decision	
Pregnancy	
Protocol deviation	
Screen failure	
Site terminated by sponsor	
Study terminated by sponsor	
Withdrawal by subject	

7.1. Discontinuation of Study Intervention

If a participant does not tolerate study injections, the participant will be observed until the intolerance has either resolved or satisfactorily stabilized in the judgement of the investigator and the participant may choose to exit the study or to remain in the study for all safety follow-up assessments through the EOS Visit.

If a pregnancy is confirmed after the participant has received study intervention, the participant may choose to exit the study after appropriate safety follow-up or to remain in the study for all safety and efficacy follow-up assessments through the EOS visit.

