9.3. Populations for Analyses

The 2 analysis populations are defined below:

- The mITT population includes all randomized participants with ≥ 1 postbaseline assessment for the primary efficacy endpoint. Participants will be summarized according to the randomized study intervention.

BOTOX

- The safety population includes all randomized participants who are administered study intervention. Participants will be summarized according to the study intervention they received.

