### 6.0 PARTICIPANT POPULATIONS

## 6.1 MODIFIED INTENT-TO-TREAT POPULATION

The modified intent-to-treat (mITT) population will consist of all randomized participants who had at least 1 post-baseline assessment of the primary efficacy parameter, the C-APPS, as described in the protocol.

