#### 11.0 EFFICACY ANALYSES

The efficacy analyses will be based on the mITT population. Observed data will be used for all analyses. Baseline for efficacy is defined as the last non-missing efficacy assessment before study intervention.

The following set of hypotheses will be used to compare the BOTOX groups with placebo for the primary endpoint analysis:

 Null hypothesis: BOTOX and placebo are equally effective in the probability of achieving ≥ 1-grade improvement in the C-APPS score from baseline at Day 14.

 Alternative hypothesis: BOTOX and placebo are not equally effective in the probability of achieving ≥ 1-grade improvement in the C-APPS score
 from baseline at Day 14.

The following set of hypotheses will be used to compare the BOTOX groups with placebo for the secondary endpoint analysis:

- Null hypothesis: BOTOX and placebo are equally effective in the probability of achieving ≥ 1-grade improvement in the P-APPS score from baseline at Day 14.
- Alternative hypothesis: BOTOX and placebo are not equally effective in the probability of achieving ≥ 1-grade improvement in the P-APPS score
   from baseline at Day 14.

For the primary endpoint analysis, the Cochran-Mantel Haenszel (CMH) test will be used to evaluate the equality of responder proportions of C-APPS between study intervention groups.

The BOTOX high dose group will be compared to the placebo group, and the BOTOX low dose group will be compared to the placebo group using a gate-keeping strategy (Dmitrienko 2005). If the comparison of the BOTOX high dose group versus the placebo group yields a p-value at the 0.05 significance level, the BOTOX low dose group will then be compared with the placebo group at the same 0.05 significance level. Otherwise, the BOTOX low dose group will not be considered statistically significantly superior to the placebo group, regardless of its p-value. (see Section 11.3.)

Similarly, for the secondary endpoint analysis, the statistical comparisons will be conducted for the P-APPS.

All statistical tests will be 2-sided hypothesis tests performed at the 0.05 level of significance for main effects. Wald confidence intervals for proportions of responders and difference in the proportion of responders will also be presented. All confidence intervals will be 2-sided 95% confidence intervals.

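### Protocol 7.1 leaves out efficacy ratings for participants who do not tolerate the injections; read literally, it can leave their Day 14 C-APPS and P-APPS missing

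*Protocol*

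**What the plan says.** Protocol Section 7.1 has two short paragraphs. The first covers intolerance of the study injections: after observation, the participant may exit or "remain in the study for all safety follow-up assessments through the EOS Visit". The second covers pregnancy confirmed after dosing: that participant may exit or "remain in the study for all safety and efficacy follow-up assessments through the EOS visit".

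The Schedule of Activities (Protocol Section 1.2) marks C-APPS and P-APPS at every post-baseline visit, including Study Exit. Footnote b applies the Study Exit column to early discontinuation and asks for all exit assessments. Section 8 makes adherence to the schedule a requirement of study conduct.

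On the analysis side, the protocol (Section 9.3) defines mITT as "all randomized participants with ≥ 1 postbaseline assessment for the primary efficacy endpoint", and SAP Section 6.1 asks for "at least 1 post-baseline assessment of the primary efficacy parameter, the C-APPS". The primary timepoint is Day 14, with an analysis window of Days 11 to 21 (SAP Table 16-1). SAP Section 11.0 states: "Observed data will be used for all analyses". The readable text has no imputation or non-responder rule for a missing rating.

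**The concern.** The two paragraphs of 7.1 deal with similar situations and differ in one respect: efficacy is named for pregnancy and not for intolerance. A site could reasonably take the difference as deliberate. The protocol also keeps the two categories apart. C-APPS and P-APPS belong to Section 8.1 (Efficacy Assessments), while Section 8.2 (Safety Assessments) covers height and weight, vital signs and pregnancy testing. On its face, a promise of safety assessments does not include either scale.

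If ratings stop, the primary and secondary outcomes go missing because of something that happened after randomisation and is tied to the injection. The frequency of such events may differ between the high dose, the low dose and placebo. The Day 14 comparison would then rest on a subset selected partly by tolerability. Unlike most missing data, these values could be collected, because participants who remain are still attending the visits.

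**Working it through.** **1. The plan's own figure.** Both documents give about 165 enrolled, 1:1:1, so 165 / 3 = 55 per arm, with 10% attrition. 165 × (1 − 0.10) = 148.5, stated as 148, which reproduces. The allowance is one overall figure, and nothing says how much of it is due to intolerance.

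**2. What happens to an intolerant participant.** Treatment is given once, on Day 1. The result depends on which text the site follows.

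| Path | Day 14 C-APPS | mITT |
|---|---|---|
| Remains, site follows the schedule | collected | in |
| Remains, site follows 7.1 literally, no post-baseline C-APPS at all | missing | out |
| Remains, site follows 7.1 literally, but a C-APPS was taken earlier (e.g. Day 7) or is taken at Study Exit | missing if ratings stopped before Day 14 | in |
| Exits on Days 2 to 10, exit C-APPS done | missing (rating maps to Day 7) | in |
| Exits on Days 11 to 21, exit C-APPS done | exit rating can serve | in |

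The consequence common to the literal paths is a missing Day 14 value. Loss from mITT needs the further condition that no other post-baseline C-APPS exists.

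**3. Illustrative size.** Assumptions: 55 in a BOTOX arm, true response rate r, and k intolerant participants without a Day 14 rating. The values of r and k are not in the documents.

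If all k are non-responders, the reported rate is 55r / (55 − k):

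| r | k = 1 | k = 2 | k = 3 |
|---|---|---|---|
| 50% | 27.5/54 = 50.9% | 27.5/53 = 51.9% | 27.5/52 = 52.9% |
| 30% | 16.5/54 = 30.6% | 16.5/53 = 31.1% | 16.5/52 = 31.7% |

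If all k are responders, the reported rate is (55r − k) / (55 − k). At r = 50% this is 26.5/54 = 49.1% for k = 1 and 24.5/52 = 47.1% for k = 3, so the sign reverses.

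A second way to see the size is to take an observed rate p and compare it with the rate when the k missing participants count as non-responders. The gap is p × k/55. For p = 50% it is 0.9, 2.7 and 4.5 points at k = 1, 3 and 5. For p = 70% it is 1.3, 3.8 and 6.4 points.

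**4. Scale.** The Wald 95% half-width for one arm of 55 at 50% is 1.96 × √(0.5 × 0.5 / 55) = 0.132, about 13 points. With k of 1 to 3, the shift is well inside sampling error.

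**The case against.** The strongest reply is that the schedule already settles the matter. Section 7.1 does not contain the word *only* and does not say that C-APPS stops. The schedule lists the rating at every visit, footnote b requires it at early exit, Section 7 asks withdrawn participants to complete the early withdrawal activities, Section 7.2 points to the schedule for data at discontinuation, and Section 8 makes the schedule mandatory. This carries weight: a site following the schedule loses nothing. It does not remove the problem, because no text says whether the general schedule or the specific sentence in 7.1 prevails, and the neighbouring paragraph shows that the authors named efficacy when they meant it.

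Three stronger readings might be inferred, and the documents do not support them.

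- *Intolerant participants fall out of mITT.* One C-APPS at any post-baseline visit is enough, and an exit rating or an earlier Day 7 rating supplies it.
- *BOTOX response rates are biased upward.* That assumes those lost are non-responders and sit mainly in the BOTOX arms. SAP Section 12.1 lists needle-related pain and anxiety among procedure-related events, and these can occur on placebo. Nothing in the documents shows how intolerant participants respond.
- *Section 6.5 contradicts the retention aim.* Users of prohibited medication "may be discontinued from the study at the discretion of the investigator or the sponsor", while the opening of Section 7 says "Every effort should be made to retain participants in the study until completion as much as possible". The first is permissive and the second is a goal qualified by what is possible. They can stand together.

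It is also fair to say that a sensitivity analysis counting missing Day 14 ratings as non-response would cover the gap whatever its cause. That would complement the change to 7.1, but an obtainable rating is better than an assumption about it.

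**Conclusion.** The point holds as an inconsistency between Section 7.1 and the Schedule of Activities. Under the literal reading, the Day 14 C-APPS and P-APPS can be lost after an event tied to treatment, and the observed-data rule then drops the participant from the primary and secondary comparisons. Exclusion from mITT is conditional. The size and direction of any bias cannot be determined, because the documents give neither an intolerance rate nor the response of such participants. The illustrative shifts rest on assumed values of r, p and k and on an assumed placement of all losses in one BOTOX arm; for a few participants they are small. This is a low-cost improvement that protects the randomised Day 14 comparison, not a flaw that undermines the trial.

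**What to change.** Amend the first paragraph of Protocol Section 7.1 so that a participant who does not tolerate the injections and agrees to stay is followed for efficacy as well as safety, in the terms already used for pregnancy, and so that the paragraph agrees with the Schedule of Activities. Scheduled C-APPS and P-APPS ratings then continue, and these participants are analysed in the arm to which they were randomised, as Protocol Section 9.3 already provides for mITT.

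The change concerns outcome collection only. The participant's choice to exit and all care decisions stay as they are.

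Cost: a wording change in one sentence, plus one clinician rating and one self-rating per visit for a small number of participants who are attending anyway. Limit: participants who choose to exit are not recovered beyond the exit assessment already scheduled.

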7.2. Participant Discontinuation/Withdrawal from the Study

- A participant may withdraw from the study at any time at his/her own request or may be withdrawn at any time at the discretion of the investigator for safety, behavioral, compliance, or administrative reasons.

BOTOX

- If the participant withdraws consent for disclosure of future information, the sponsor may retain and continue to use any data collected before such a withdrawal of consent.
- See the SoA for data to be collected at the time of study discontinuation and follow-up and for any further evaluations that need to be completed.

7.3. Lost to Follow Up

A participant will be considered lost to follow-up if he/she repeatedly fails to return for scheduled visits and is unable to be contacted by the study site.

The following actions must be taken if a participant fails to return to the clinic for a required study visit:

- The site must attempt to contact the participant and reschedule the missed visit as soon as possible and counsel the participant on the importance of maintaining the assigned visit schedule and ascertain whether or not the participant wishes to and/or should continue in the study.
- Before a participant is deemed lost to follow-up, the investigator or designee must make every effort to regain contact with the participant (where possible, 3 telephone calls and, if necessary, a certified letter to the participant's last known mailing address or local equivalent methods). These contact attempts will be documented in the participant's medical record.
- Should the participant continue to be unreachable, he/she will be considered to have withdrawn from the study.

[figure not shown]
[figure not shown]
8. Study Assessments and Procedures

- Study procedures and their timing are summarized in the SoA (Section 1.2).
- Protocol waivers or exemptions are not allowed.
- Immediate safety concerns should be discussed with the sponsor immediately upon occurrence or awareness to determine if the participant should continue or discontinue study intervention.
- Adherence to the study design requirements, including those specified in the schedule of assessments, is essential and required for study conduct.
- All screening evaluations must be completed and reviewed to confirm that potential participants meet all eligibility criteria. The investigator will maintain a screening log to record details of all participants screened and to confirm eligibility or record reasons for screening failure, as applicable. During the Screening Period, the investigator or subinvestigator will assess the clinical significance of any physical examination findings. Any participants with abnormalities judged to meet exclusion criteria will be excluded from the study.

8.1. Efficacy Assessments

8.1.1. Primary Efficacy Assessment

Prior to enrolling participants, investigators (or subinvestigators when applicable) will be trained in grading platysma prominence severity using the C-APPS.

8.1.2. Secondary Efficacy Assessment

BOTOX

[REDACTED]

[REDACTED]

[REDACTED]

8.2. Safety Assessments

Planned timepoints for all safety assessments are provided in the SoA (Section 1.2).

[REDACTED]

[REDACTED]

8.2.2. Vital Signs

Vital signs will be assessed as follows:

Pulse rate, blood pressure, and respiratory rate will be assessed with participants in a sitting position; use of either a manual or automated device is acceptable.

- Pulse rate (beats per minute): Participants are to be seated for at least 5 minutes, and pulse will be counted over 60 seconds and recorded in the source document and eCRF as beats per minute.
- Blood pressure (mm Hg): Participants are to be seated for at least 5 minutes and systolic and diastolic blood pressure will be measured.
- Respiration rate (breaths per minute): Participants are to be seated for at least 5 minutes and breaths will be counted for 30 seconds and multiplied by 2.

8.2.3. Pregnancy Testing

Women of childbearing potential (WOCBP) must have a negative urine test result before receiving study intervention. A urine pregnancy test may also be performed at any other visit, at the investigator's discretion.

8.3. Adverse Events and Serious Adverse Events

The definitions of an AE or SAE can be found in [Appendix 3](#).

AEs will be reported by the participant (or, when appropriate, by a caregiver or surrogate).

BOTOX

The investigator and any qualified designees are responsible for collecting, detecting, documenting, and recording events that meet the definition of an AE or SAE and any other study-specific term as relevant and remain responsible for following up AEs that are serious, considered related to the study intervention or study procedures, or that caused the participant to discontinue the study (see Section 7).

8.3.1. Time Period and Frequency for Collecting Adverse Event and Serious Adverse Event Information

All SAEs from the signing of the ICF until the follow-up visit will be collected at the timepoints specified in the SoA (Section 1.2), and as observed or reported spontaneously by study participants.

All AEs from the signing of the ICF until the follow-up visit will be collected at the timepoints specified in the SoA (Section 1.2), and as observed or reported spontaneously by study participants.

Medical occurrences that begin before the start of study intervention, but after obtaining informed consent will be recorded in the AE section of the eCRF.

All SAEs will be recorded and reported to the sponsor or designee within 24 hours of awareness, as indicated in [Appendix 3](#). The investigator will submit any updated SAE data to the sponsor within 24 hours of it being available.

AESIs are described below in Section 8.3.6 and in [Appendix 3](#).

Investigators are not obligated to actively seek AE or SAE information after conclusion of the study participation. However, if the investigator learns of any SAE, including a death, at any time after a participant has been discharged from the study, and he/she considers the event to be reasonably related to the study intervention or study participation, the investigator must promptly notify the sponsor.

The method of recording, evaluating, and assessing causality of AEs and SAEs and the procedures for completing and transmitting SAE reports are provided in [Appendix 3](#).

8.3.2. Method of Detecting Adverse Events and Serious Adverse Events

Care will be taken not to introduce bias when detecting AEs and/or SAEs. Open-ended and non-leading verbal questioning of the participant is the preferred method to inquire about AE occurrences.

8.3.3. Follow-up of Adverse Events and Serious Adverse Events

After the initial AE/SAE report, the investigator is required to proactively follow each participant at subsequent visits/contacts. All SAEs and AESI (as defined in Section 8.3.6) will be followed until resolution, stabilization, the event is otherwise explained, or the participant is lost to follow-up (as defined in Section 7.3).

BOTOX

The investigator is obligated to perform or arrange for the conduct of supplemental measurements and/or evaluations as medically indicated or as requested by the sponsor to elucidate the nature and/or causality of the AE or SAE as fully as possible. This may include additional laboratory tests or investigations, histopathological examinations, or consultation with other health care professionals.

If a participant dies during participation in the study or during a recognized follow-up period, the investigator will provide the sponsor with a copy of any postmortem findings including histopathology.

New or updated information will be recorded in the originally completed eCRF.

The investigator will submit any updated SAE data to the sponsor within 24 hours of receipt of the information.

8.3.4. Regulatory Reporting Requirements for Serious Adverse Events

- Prompt notification by the investigator to the sponsor of an SAE is essential so that legal obligations and ethical responsibilities towards the safety of participants and the safety of a study intervention under clinical investigation are met.
- The sponsor has a legal responsibility to notify both the local regulatory authority and other regulatory agencies about the safety of a study intervention under clinical investigation. The sponsor will comply with country-specific regulatory requirements relating to safety reporting to the regulatory authority, IRBs/ IECs, and investigators.
- Investigator safety reports must be prepared for SUSARs according to local regulatory requirements and sponsor policy and forwarded to investigators as necessary.
- An investigator who receives an investigator safety report describing an SAE or other specific safety information (eg, summary or listing of SAEs) from the sponsor will review and then file it along with the IB and will notify the IRB/IEC, if appropriate according to local requirements.

